9. STUDY TIMELINES

- *Describe the duration of an individual's participation in the study*
- *Describe the duration anticipated to enroll all study subjects*
- *The estimated date of study completion*

The study will take place over the course of 14 weeks. The first two weeks will be a baseline period, where no light therapy is assigned, but data are collected, including self-report of fatigue and accelerometer-derived sleep and activity data. After successful completion of the baseline period, participants will be randomized to six 2-week treatment blocks of bright blue light therapy, dim blue light therapy, and usual care. In usual care treatment periods, participants will be instructed to not use any light therapy device and will be asked to continue answering survey questions and wearing their Fitbit device. At the end of the 14 weeks, a report containing the individual's analyzed data will be sent to each participant, along with a satisfaction survey. This report will be sent within 3 months of study completion. After the satisfaction survey is completed, study coordinators will reach out to each participant to interview them about their experience in Personalized Trials. A \$100 pay card (CliniCard) will be mailed to each participant as compensation for their time after the successful completion of 14 weeks of data collection, satisfaction survey, and phone interview.

Potential participants will have the opportunity to choose from within a provided list of start dates during their enrollment process. No more than 20 potential participants will begin their baseline period on the same day. Enrollment will be ongoing until up to 60 participants have been randomized after baseline to receive a personalized trial of light therapy for self-reported fatigue. We estimate that the final participant will be randomized by September 30, 2021, and data collection will cease by December 31, 2021.

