Participants may receive additional text messages to those outlined above with important reminders about their protocol (e.g. transition to a new treatment period), or to remind participants to sync their data. We will send a maximum of 6 text messages per day during the study, including these reminders and the survey questions outlined above.

In the event of an unanticipated circumstance that temporarily prevents a participant from completing study activities (illness, injury, death in the family, etc.), the participant will have the option of pausing their study to resume once their circumstance has been positively resolved.

Participants will complete remote data monitoring after they have gone through one baseline period (two weeks), two bright blue light therapy periods (two weeks each), two dim blue light therapy periods (two weeks each), and two usual care periods (two weeks each), or 14 weeks total. Alternatively, a participant may choose to withdraw from the study, or be withdrawn from the study by the research team. Upon completion of data monitoring, participants will be given instructions on how to un-link their Fitbit from the study account. Daily text messages and survey prompts will be cancelled for participants who are withdrawn from the study.

We will compile the self-reported data from questionnaires, treatment adherence, side effects, pain, fatigue, concentration, confidence, mood, and stress assessments, as well as information from the Fitbit regarding activity (steps, flights climbed and intensity), sleep (duration, estimated sleep stages) for each individual participant. Treatment adherence will be tracked via an AYO research web portal and will be included in the compiled data. No identifying information will be provided to AYO or included on the treatment adherence report provided by AYO. We will analyze this data and create a summary report of the participant's data and symptoms over the study period, relation to the bright blue light therapy, dim blue light therapy, and usual care treatment periods.

The participant will be sent this report in an encrypted email and secure web link by our study team. Participants will also be sent links to several online videos explaining the terms and data visualizations available in their summary report. These videos will be general to the template report and will not contain any

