individual results or health information. Participants will be sent a satisfaction survey along with their individual report.

The satisfaction survey will be sent via email up to two times before a research coordinator will attempt to call individual participants to complete the satisfaction survey via phone. Participants will be mailed a pay card (Clinicard) valued at \$100 after successful completion of the satisfaction survey.

Within 3 months of an individual ending their remote data monitoring, regardless of when that takes place, participants will be asked to schedule a phone call from a member of our study team to discuss their study experience. We will ask several questions about their experience and opinion toward Personalized Trials, as well as for suggestions for improvement for future Personalized Trials. Study participation will end after successful completion of this participant phone interview.

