The randomization schedule will be set up by a member of the Center for Personalized Health data team and provided to the data analyst assigned to Personalized Trials of Light Therapy for Fatigue. Randomization will occur with a fixed seed value for the purposes of repeatability and auditability, and the list of 60 participants will be split into two groups of 30 using a random shuffle function that takes that seed as input. The order in which an individual becomes eligible for one of these 60 randomizations will determine the placement given (i.e. the first person eligible will be randomized to the treatment order given to participant 1, and continue sequentially). Eligibility is obtained by a participant maintaining at least 80% adherence of survey response, Fitbit wear \geq 12 hours a day, and 80% sleep data available through the baseline run-in period. The data analyst will alert the research coordinator of the assigned randomization once a participant becomes eligible during the baseline run-in period.

The primary outcome measure will be a mean usability score, obtained using the System Usability Scale (SUS), a validated 10-item questionnaire originally developed by John Brooke in 1986 that asks users to score each item on a Likert scale from Strongly Disagree (rating of 1) to Strongly Agree (rating of 5). The SUS will be presented to the participant as addressing the ease of use, complexity, consistency of the Personalized Trials system as a whole, from recruitment to receipt of the report. Individual results are calculated to arrive at a composite measure out of 100. Participant SUS scores will be averaged together. Higher scored values correlate to a more usable system, and therefore a better outcome.

Other outcome measures assessing feasibility of the Personalized Trials framework include:

- Mean participant satisfaction with Personalized Trials components supplemental to the SUS,
- Qualitative satisfaction data collected during the participant phone interview,
- Mean participant survey adherence rate, defined as completion of each assigned survey
- Mean participant Fitbit adherence rate, defined as recorded heart rate data for \geq 12 hours each day,
- Mean participant Fitbit sleep rate, defined as recorded sleep and wake cycles
- Mean participant bright AYO adherence rate, defined as completion of each assigned 30-minute session
- Mean participant dim AYO adherence rate, defined as completion of each assigned 30-minute session

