Should a participant choose to withdraw from research, they will be instructed to send a letter or e-mail to the attention of the Principal Investigator at our [name] office, or to email [contact], an e-mail account monitored by IRB-approved members of the research team. Participants will be contacted by a member of the research team confirming their study withdrawal, and to answer any questions they may have. The participant will stop receiving notification and survey prompts, and will be sent instructions to un-link their Fitbit device. Data collection will stop the business day the letter or email is received. All data up until the receipt date of the letter will be included in the research study.

Partial withdrawal, defined as study participation and data collection without the use of one of the light therapy devices will be allowed if a participant experiences an adverse events to one of the treatment options (bright blue light or dim blue light therapy). In instances where participants contact the research team with concerns about their self-reported treatment side-effects, participants will be permitted to continue their involvement in the study, should they be interested. Participant data will continue to be collected and monitored, while removing the self-reported adverse treatment option from their randomized protocol (i.e. skip the treatment days and continue with usual care). This will allow the participant to still evaluate their individual response to the self-reported non-aggravating treatment option. In the event that both treatment options create self-reported adverse events for the participant, they will be withdrawn from the study.

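### Mean SUS, the named primary outcome measure, appears to be collected only with or after the report, so it probably describes those who stayed and may overstate usability

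*Combined protocol and SAP*

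**What the plan says.** Section 12 states: "The primary outcome measure will be a mean usability score, obtained using the System Usability Scale (SUS". The scale is presented as rating the "Personalized Trials system as a whole, from recruitment to receipt of the report". The summary rule is "Participant SUS scores will be averaged together". No denominator, rule for missing scores or sensitivity analysis is given.

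On timing, Section 9 says that at the end of the 14 weeks a report of the individual's "analyzed data will be sent to each participant, along with a satisfaction survey". Section 11 repeats this: "Participants will be sent a satisfaction survey along with their individual report". Non-response is followed up: "The satisfaction survey will be sent via email up to two times before a research coordinator will attempt to call individual participants".

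On leaving early, Section 11 says: "Daily text messages and survey prompts will be cancelled for participants who are withdrawn from the study". Section 16 likewise ends notifications and survey prompts for those whom the team withdraws. For those who choose to leave, it says: "Data collection will stop the business day the letter or email is received". Grounds for removal without consent in Section 16 include poor protocol adherence, repeatedly missed light sessions and self-reported side effects.

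**The concern.** The pilot asks whether the whole Personalized Trials system is usable and acceptable. People who leave, or who are removed because they did not keep up with surveys, wearable or light sessions, may include many who found the system hard to use. If they are never asked for a SUS score, a plain average of returned scores describes the people for whom the system worked well enough to finish. A favourable mean could then be carried into the case for scaling up. This is a matter of collection as well as analysis: a score not obtained around the time of exit cannot be recovered later by the analysts.

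**Working it through.** **1. The plan's own figure.** No sample size, SD, target or precision is given for the SUS. The only stated calculation is for completion (Section 12): n = 60, null rate 0.50, true rate 0.70, one-sided 2.5%, about 90% power. By the normal approximation:

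(√60 × 0.20 − 1.96 × √0.25) / √0.21 = (1.549 − 0.980) / 0.458 = 1.242, so power is 89.3%.

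The stated figure is reproduced. It matters here only as the source of the 70% completion rate.

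**2. Who is likely to have a score.** Three statements have to be read together. The SUS covers the period up to receipt of the report. The satisfaction survey travels with the report. Prompts end at any withdrawal, and data collection ends at voluntary withdrawal. No section schedules a SUS at exit. If completers all respond and non-completers give no score, 0.70 × 60 = 42 scores are returned and 18 are missing.

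**3. Bias of the returned-score mean.** Let c be the share of randomised participants with a score, M1 their mean, and M0 the mean that the others would have given.

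- All-randomised mean = c × M1 + (1 − c) × M0
- Returned-score mean = M1
- Bias = M1 − [c × M1 + (1 − c) × M0] = (1 − c) × (M1 − M0)

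The identity is exact. The gap M1 − M0 is not in the documents and is an assumption throughout.

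| Share scored | Gap −5 | Gap 0 | Gap 10 | Gap 20 |
|---|---|---|---|---|
| 90% (54 of 60) | −0.5 | 0 | +1.0 | +2.0 |
| 70% (42 of 60, planning rate) | −1.5 | 0 | +3.0 | +6.0 |
| 65% (39 of 60) | −1.75 | 0 | +3.5 | +7.0 |

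The 65% row is the lowest completion at which a strict exact binomial test at 2.5% would still reject 50%: 39 or more of 60 has one-sided alpha 0.0137, while 38 or more has 0.0259.

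**4. Scale.** For an assumed SUS SD of 12 to 20, the 95% half-width with 42 scores is 1.96 × SD / √42, or 3.6 to 6.1 points. A bias of 3 to 6 points would be about as large as the sampling error, and a confidence interval for the returned scores would not show it.

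**5. Extreme bounds.** For an assumed observed mean of 75 at 70% scored, setting all missing scores to 0 gives 0.70 × 75 = 52.5. Setting them all to 100 gives 52.5 + 30 = 82.5. These limits are not realistic, but they show how little the returned scores alone fix the all-randomised mean.

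**The case against.** A reader might infer that the SUS can come only from completers, that the plan has a stated rule excluding early leavers, and that the mean is therefore biased upward. The documents do not go that far.

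- No section says which form carries the SUS, and Section 12 lists other satisfaction items as additional to it. The prompts cancelled in Section 11 may be only the daily and weekly stream; the satisfaction survey goes by email and then by coordinator call. Section 9 speaks of every participant.
- Section 11 asks for a phone interview whenever monitoring ended, and Section 9 places that interview after the survey. Early leavers might therefore be sent the survey. The stop on data collection is stated for voluntary withdrawal only.
- The direction of bias is not shown. Side effects, a listed ground for removal, need not reflect usability, and no SUS value is given for any group.
- Non-completion is not the same as a missing SUS. Participants who pause or partially withdraw can still reach the report.
- It is also tempting to take 50% completion as a rate that the plan allows. It is the null value to be rejected, so figures at 50% describe a trial that missed its completion aim.
- Someone without a report has not experienced the whole system that the SUS is meant to rate, and attrition is reported separately as the completion rate.

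Most of this stands, and it limits the point to likely selection and possible upward bias. It does not remove the point. Section 12 lists the interview as qualitative data and does not mention the SUS in it. Survey follow-up and partial withdrawal reduce losses among those who stay, not among full withdrawals. Reporting completion discloses attrition but does not correct the mean.

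**Conclusion.** The point holds in a limited form. Read together, the sections make it likely that most full withdrawals contribute no SUS score, so the planned average is probably conditional on reaching the report. Upward bias is possible, and plausible because non-adherence is itself a ground for removal, but it is not demonstrated. At the planning rate of 70%, with no scores from the 18 non-completers, the bias is 0.30 times the gap: 0, +3 or +6 points for assumed gaps of 0, 10 or 20, and negative if leavers would have rated the system higher. The size rests wholly on the assumed gap and on non-completers giving no score. Because the missing scores cannot be recovered later and the remedy is cheap, the change should be made.

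**What to change.** 1. State the SUS population and denominator, and which form carries the scale.
2. Offer the 10-item SUS, voluntarily, to every randomised participant at exit, whatever the reason. Use the contact that confirms withdrawal (Section 16) or the exit interview (Section 11), with the reference period adapted for those who have no report.
3. Amend the Section 16 sentence that stops data collection, and the consent form if needed, to permit this one optional form.
4. Report SUS returned over randomised beside the completion rate, with completer and non-completer means shown separately because their reference periods differ.
5. Add a sensitivity analysis for scores still missing, over a range of gaps that includes zero and a negative value, for example −5, 0, 10 and 20 points.

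The cost is a small protocol and possibly consent amendment, one short form at contacts already foreseen, and a brief extra analysis. The drawbacks are a slightly different reference span for early leavers and a mean SUS that may come out lower.

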Baseline participants that do not achieve at least 80% adherence of Fitbit wear and survey submission during the first 10 days of the baseline period will be withdrawn from the study. Those that maintain at least 80% adherence will be randomized to one of two treatment sequences in the pilot study. Participants who are randomized to receive treatment sequences will receive email confirmation including their protocol timeline. Participants will also receive a second mailed kit including a bright blue light commercial AYO light therapy device, and a dim blue light research AYO light therapy device. Enrollment will continue until up to 60 participants have been randomized into one of two treatment sequences.

Each treatment sequence is made up of 6 2-week periods dedicated to either bright blue light therapy, dim blue light therapy, or usual care. During both bright blue light and dim blue light therapy weeks, participants will receive a text message within an hour of their self-reported wake time instructing them to use their designated light therapy device for 30 minutes. During usual care treatment periods, participants will not receive any text notifications to complete light therapy, and will instead be asked to refrain from using either AYO device.

During all treatment weeks (12 weeks total), participants will be asked to continue wearing their Fitbit device each day and night. They will continue to receive 3 randomized text messages each day with questions about their fatigue, pain, concentration, confidence, mood, and stress at that current moment, as well as an

evening text asking them to reflect on their fatigue and any side-effects they may be experiencing from their light therapy treatment (if applicable). Participants will receive slightly longer surveys on Sunday evenings, asking them to reflect on their symptoms of fatigue that week. A study phone number and email address will be available as part of each survey to contact the study team if a participant is concerned about any side effects they are experiencing. Participants will also be instructed to stop their light therapy sessions if they are concerned about their side effects.

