- Google Ad metrics
- Social media activity, including but not limited to:
 - Social media conversion rate, defined as total impressions compared to total click-through
 - Cost per social media conversion
- Website activity, including but not limited to:

- Total number of website visits per traffic source
- Website bounce rates
- Mean user total time on website

In order to share a summary report of observed trends back to the participant to assess acceptability and satisfaction with the participant report, additional outcomes will be analyzed on an N-of-1 level including:

- Mean Within-Subject Difference in Self-Reported Daily Fatigue During 3 Treatment Periods from Mean Baseline using the PROMIS Item Bank v1.0 – Fatigue 7b Daily Short Form
- Mean Within-Subject Difference in Self-Reported Weekly Fatigue During 3 Treatment Periods from Mean Baseline, using the PROMIS Item Bank v1.0 – Fatigue 8a Short Form
- Mean Within-Subject Difference in Ecological Momentary Assessment Three-Times-Daily of Pain During 3 Treatment Periods from Mean Baseline, using the Numeric Pain Rating Scale adapted from McCaffery, Beebe et al. 1989
- Mean Within-Subject Difference in Ecological Momentary Assessment Three-Times-Daily of Fatigue During 3 Treatment Periods from Mean Baseline, using the Numeric Pain Rating Scale adapted from McCaffery, Beebe et al. 1989
- Mean Within-Subject Difference in Ecological Momentary Assessment Three-Times-Daily of Concentration During 3 Treatment Periods from Mean Baseline, using the Numeric Pain Rating Scale adapted from McCaffery, Beebe et al. 1989
- Mean Within-Subject Difference in Ecological Momentary Assessment Three-Times-Daily of Confidence During 3 Treatment Periods from Mean Baseline, using the Numeric Pain Rating Scale adapted from McCaffery, Beebe et al. 1989
- Mean Within-Subject Difference in Ecological Momentary Assessment Three-Times-Daily of Mood During 3 Treatment Periods from Mean Baseline, using the Numeric Pain Rating Scale adapted from McCaffery, Beebe et al. 1989
- Mean Within-Subject Difference in Ecological Momentary Assessment Three-Times-Daily of Stress During 3 Treatment Periods from Mean Baseline, using the Numeric Pain Rating Scale adapted from McCaffery, Beebe et al. 1989
- Mean Within-Subject Difference in Self-Reported Side Effects from Baseline, using the average number of days side effects were reported during treatment periods.

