This pilot study will use Fitabase to retrieve Fitbit data from participants. Fitabase is a secure, online portal. The Fitbit study account provided to the participants will be linked to an identification number in the Fitabase system (e.g. FLT01). No information that could be used to identify a participant will be stored on Fitabase. Only the research team will have access to data that will be able to connect a research participant to their Fitabase ID. Data collected will include last sync date, battery charge status, daily steps, floors climbed, activity intensity, sleep duration, and estimated minutes in sleep stages. Fitabase will stop tracking participant data at the trial end date selected by the research coordinator. As an added measure, participants will be instructed to remove the Fitbit study account from their device if they plan on keeping the Fitbit.

Treatment Delivery

This pilot study will use commercially-available bright-blue light therapy glasses called AYO, as well as a dim blue light therapy device developed by AYO for research purposes. The research team will have access to a dashboard that will track light therapy device used (bright/full or dim), duration, and date and time based on a generic application user ID (e.g. Northwell_001). No information that could be used to identify a participant will be stored on the AYO research web portal, nor on the AYO device itself. Only the research team will have access to data that will be able to connect a research participant to their generic AYO user ID.

Eligibility, Consent, and Survey Data

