16. WITHDRAWAL OF SUBJECTS

- *Describe anticipated circumstances under which subjects will be withdrawn from the research without their consent*
- *Describe procedures for orderly termination*
- *Describe procedures that will be followed when subjects withdraw from the research, including partial withdrawal from procedures with continued data collection.*

Circumstances under which participants will be withdrawn from the research without their consent include failure to maintain protocol adherence, repeated failure to complete light therapy treatments, and self-reported adverse side effects to bright blue light or dim blue light therapy. A potential participant will not be randomized to receive the treatment protocol until he/she has demonstrated at least 80% adherence to continuous Fitbit monitoring (activity recorded > 12 hours/day, and recorded sleep activity) and response to survey questionnaires during the baseline period.

Potential participants will be notified of the possibility of being removed from the study before treatment randomization due to adherence issues in the informed consent. Participants who fail to maintain minimum adherence during baseline will be notified by the research team after 10 days of baseline participation.

Participants who fail to maintain protocol adherence or who deviate from the protocol will be contacted by a member of the study team with a reminder of the study protocol, and warning that this may impact their continued study eligibility. Once a protocol deviation has been repeatedly recorded, the Principal Investigator will determine the participant's continued eligibility in the study, with consultation of the DSMB if needed. If it is determined that the participant will be withdrawn from the study, the participant will be notified by the research team via email and phone call. The participant will stop receiving notifications and survey prompts, and will be sent instructions to un-link their Fitbit device. The participant will be able to keep their Fitbit and one of the AYO light therapy devices.

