17. RISKS TO SUBJECTS

- *Describe any potential risks and discomforts to the subject (physical, psychological, social, legal, or other) and assess their likelihood and seriousness and whether side effects are reversible. Where appropriate, describe alternative treatments and procedures that might be advantageous to the subjects.*
- *Include risks to others , like sexual partners (if appropriate)*
- *Discuss why the risks to subjects are reasonable in relation to the anticipated benefits and in relation to the importance of the knowledge that may reasonably be expected to results*
- *Describe the procedures for protecting against or minimizing any potential risks, including risks to confidentiality, and assess their likely effectiveness.*

This study poses low risk of physical harm to subjects. Bright blue light therapy is a mainstream treatment for fatigue symptoms. Several transient side-effects have been observed when monitoring patients including jumpiness/jitteriness, headache, and nausea, and mania has been infrequently observed in patients with bipolar disorder. These side-effects typically resolve soon after cessation of light therapy. Monitoring for adverse side-effects will be performed during the N-of-1 trial. Subjects will be encouraged to adhere to the light therapy protocol, but will also be told that they can discontinue treatment at any time.

AYO glasses have 4 Light-emitting diodes (LEDs) with a dominant wavelength of approximately $470\text{nm} \pm 2\text{nm}$ and typical irradiance (100% intensity) of approximately $250\text{ }\mu\text{W/cm}^2$. Although there are minimal direct safety standards for blue light within the United States, the photochemical blue light hazard can be evaluated based on several global standards. AYO glasses are compliant with the following: Directive 2014/30/EU (EMC) EN 55014-1:2006 + A2:2011 EN 55014-2:2015, Directive 2011/65/EU (RoHS), IEC 62321:2008, IEC 62321-3-1:2013, IEC 62321-4:2013, IEC 62321-5:2013, Radio-Equipment Directive 2014/53/EU, EN 62479:2010, EN 300328:2015, EN 301489-1:2011, EN 301489-17:2012, RoHS Directive 2011/65/EU of the European Parliament, the Council from 08/06/2011 on restriction of the use of certain hazardous substances in electrical and electronic appliances, and with the international standard and conformity assessment IEC 62471 “Photobiological safety of lamps and lamp systems.”

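### The side-effect outcome counts days reported with no denominator of exposed days, so it understates side effects for a device stopped early and can rank that device as the better tolerated one

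*Combined protocol and SAP*

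**What the plan says.** Section 12 (Statistical Analysis) lists one side-effect outcome among those analysed for each participant's report. It is a mean within-subject difference from baseline, "using the average number of days side effects were reported during treatment periods". The unit of averaging is not stated, and no rule covers stopped or skipped days.

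Section 11 (Research Procedures) schedules "two bright blue light therapy periods (two weeks each), two dim blue light therapy periods (two weeks each"). It collects side effects in the evening text, where applicable. It also states: "Participants will also be instructed to stop their light therapy sessions if they are concerned about their side effects".

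Section 16 (Withdrawal of Subjects) allows a participant to continue, with data still collected, after "removing the self-reported adverse treatment option from their randomized protocol (i.e. skip the treatment days and continue with usual care"). The same section names "self-reported adverse side effects to bright blue light or dim blue light therapy" among the circumstances for withdrawal without consent.

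Section 17 (Risks to Subjects) says of the known effects: "These side-effects typically resolve soon after cessation of light therapy".

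Exposure is recorded. Section 14 describes a dashboard that will "track light therapy device used (bright/full or dim), duration, and date and time". Section 12 lists bright and dim adherence as separate outcomes, but links neither to the side-effect line.

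**The concern.** The number of days on which a side effect can be reported depends on how long the device is used, and the plan lets side effects themselves shorten that use. A participant who tolerates a device badly may use it for a few days and then add nothing more to the count. A participant who tolerates it fairly well can go on adding days for four weeks. Without exposed days as a denominator, a low figure may mean good tolerability or early stopping.

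The report goes to participants, and Section 2 says the study will look at whether they can choose a preferred intervention from it. Section 3 presents information on side effects as one of the benefits of N-of-1 trials. Sections 4 and 14 foresee pooling N-of-1 results, so the same distortion could carry into any pooled tolerability summary.

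**Working it through.** The plan states no figure for this outcome, so there is none to reproduce. The check is arithmetic on how the measure behaves.

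**Inputs**
- Scheduled days per device: 2 periods × 14 days = 28 (Section 11).
- Side-effect days after stopping: taken as zero, in line with Section 17.
- Side-effect rate per exposed day: not in the documents. Assumed range is 0.3 to 1.0 for the worse device (rate A) and 0.1 to 0.3 for the other (rate B).
- Device A is stopped after k exposed days. Device B is used on all 28.

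**Step 1: against full use of the same device.** The expected count falls from rate A × 28 to rate A × k. The share kept is k/28: 3/28 = 10.7% for a stop after day 3, and 14/28 = 50% for a stop after day 14. This holds at any rate.

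**Step 2: against the other device, on a total count.** A ranks as better although its rate is higher when rate A × k < rate B × 28, that is, when k < 28 × (rate B ÷ rate A). Break-even exposed days:

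| Rate A | Rate B 0.1 | Rate B 0.2 | Rate B 0.3 |
|---|---|---|---|
| 1.0 | 2.8 | 5.6 | 8.4 |
| 0.75 | 3.7 | 7.5 | 11.2 |
| 0.5 | 5.6 | 11.2 | 16.8 |
| 0.3 | 9.3 | 18.7 | equal rates |

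Among the 11 pairs with unequal rates, a stop after day 3 reverses the order in 10. The exception is 1.0 against 0.1 (3.0 against 2.8 days). A stop after day 14 reverses it in only two: 0.5 against 0.3 (7.0 against 8.4) and 0.3 against 0.2 (4.2 against 5.6).

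**Step 3: one participant under different averaging units.** Bright has side effects on 3 of 3 days and is then removed. Dim has them on 5 of 28 days.
- Total count: 3 against 5. Bright looks better.
- Per assigned day: 3/28 = 10.7% against 5/28 = 17.9%. Bright looks better.
- Per two-week period, skipped block scored as zero: 3/2 = 1.5 against 5/2 = 2.5. Bright looks better.
- Per two-week period, skipped block dropped: 3/1 = 3.0 against 5/2 = 2.5. Bright is correctly worse.
- Per exposed day: 3/3 = 100% against 5/28 = 17.9%. Bright is correctly worse.

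**Step 4: does dropping skipped blocks cure it?** If A is stopped within its first block, the comparison becomes rate A × k against rate B × 14, so the break-even halves to 14 × (rate B ÷ rate A). For 0.5 against 0.2 it is 5.6 days instead of 11.2. In the Step 3 example, 6 dim days give a tie (3.0 against 6/2 = 3.0), and 7 dim days reverse the order (3.0 against 7/2 = 3.5) although the rates are 100% and 7/28 = 25%. The bias is smaller but still there, because the block in which stopping occurs is itself cut short.

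**The case against.** The strongest reply is that Section 12 does not define a total out of 28. Baseline and every treatment block last two weeks, so a mean per two-week period is an equally natural reading. With skipped blocks dropped, it ranks the Step 3 example correctly. That stands as far as it goes: the unit is unspecified, and this reading lessens the problem. Step 4 shows that it does not remove it.

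A reader might infer that an early-stopped device will always score as better tolerated than the other. The documents do not support that. Reversal needs stopping before the break-even, and no side-effect rate or stopping frequency is given. Only the understatement relative to full use of the same device is general.

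A reader might also infer that side effects will never be shown by device. Section 11 says side effects and adherence are both compiled, and that the report relates the data to the bright, dim and usual-care periods. The per-device adherence rates would partly reveal early stopping, though not the reason for it. A participant who asked for a device to be removed will also remember why. What remains is that the side-effect figure itself carries no exposure.

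Finally, Section 17 has the DSMB review adverse-outcome data at least yearly. Safety oversight therefore does not rest on this line.

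**Conclusion.** The concern holds in a conditional form. As written, the outcome understates side effects for a device stopped early because of them, under any averaging unit that does not use exposed days. It can misrank the two devices when stopping comes before about 28 × (rate B ÷ rate A) exposed days on a total count. The limit is half that for a first-block stop on a per-period mean that drops skipped blocks. Over the assumed rates, the total-count limit runs from 2.8 to 18.7 days.

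This rests on illustrative rates, on no side-effect days after stopping, and on full use of the other device. The effect is confined to the participant report and any pooled tolerability summary. A reader might infer a threat to the trial's main conclusion, but neither trial completion (Section 10) nor the usability score (Section 12) uses this measure. The change is worth making but is not critical.

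**What to change.** Rewrite the side-effect line in Section 12 as follows.

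1. **Within participant, for bright and dim separately:** side-effect days divided by days with both a portal-logged session on that device and an answered evening survey. Show numerator and denominator. Count a logged session of any duration, so that a session cut short by a side effect stays in.
2. **Across participants:** total side-effect days over total exposed days, or a model weighted by exposed days, and not an unweighted mean of individual rates. For two people with 1/1 and 2/28, the unweighted mean is (100% + 7.1%)/2 = 53.6%, while the pooled figure is 3/29 = 10.3%.
3. **Always alongside:** the number and proportion who stopped or had that device removed because of side effects, with exposed days at stopping. This is essential because the pooled figure gives early stoppers little weight.
4. **Contrast:** use the usual-care periods, provided the evening text asks about side effects then; Section 11 limits the question to where it applies. Use baseline only if the baseline evening survey asks it; Section 11 describes fatigue questions only.

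Section 16's listing of side effects as a reason for withdrawal and its allowance for partial withdrawal should also be reconciled, so that it is clear which participants supply data after stopping.

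The cost is a rewritten outcome line and a merge of the evening survey with the portal log. The downside is that rates from few exposed days are imprecise and are pushed upward when a side effect triggers stopping (1/1 = 100%), which is a further reason to show the stopping figure with them.
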